CHAGNING HABITS AND LIFESTYLES IN OLDER INDIVIDUALS

Registration: NCT02777918

Date of Document: 26.07.2018

INCREASING EGG AND DIETARY PROTEIN INTAKE IN COMMUNITY-DWELLING OLDER ADULTS USING RECIPES AND SINGLE-USE HERB / SPICE PACKETS: A RANDOMIZED CONTROLLED TRIAL

METHODS

The study used a parallel group, randomized controlled intervention design, where community-dwelling older adults were randomized to receive or not receive high-protein egg-based recipes and herb/spice packets for 12 weeks, and egg intake, protein intake, and measures of health and well-being were measured at baseline, at the end of 12 weeks and after a further 12 weeks.

Participants

Older adults were considered for inclusion in the study if they were: 55 years and over; living in the community; not allergic to eggs; not knowingly suffering from hypercholesterolaemia or familial hypercholesterolaemia; not knowingly suffering from known renal insufficiency; not having undergone chemotherapy or radiotherapy in the last 6 months; not suffering from any condition, or receiving treatment that affected eating or sense of flavour; were able to give consent and complete all questionnaire measures; and did not have a pacemaker or defibrillator. These inclusion criteria allowed inclusion of volunteers within our target population (older adults living in the community), while ensuring against adverse health consequences as a result of a change in eggs or dietary protein consumption (British-Heart-Foundation, 2015; Pedrini, Levey, Lau, Chalmers, & Wang, 1996) or involvement in the study, and valid outcome assessments (Jacobsen et al., 1993; Steinbach et al., 2009; Van Cutsem & Arends, 2005).

Sample size:

Data from the National Diet and Nutrition Survey (NDNS) show that UK adults over 65 years old have a mean daily protein intake of 69.8g (SD = 20.3) (Bates et al., 2014). Assuming a threshold to stimulate muscle protein synthesis of 25-30g protein per meal (Paddon-Jones & Rasmussen, 2009) for three meals per day, daily intake should be at least 75-90g per day, an increase of on average 12.7g of protein per day. Assuming no change in the control group over the intervention period, and an alpha of 5% for a power of 0.8, the required sample size to detect a 12.7g increase in protein intake in the intervention group equals 41 participants per group. Taking into account a possible drop-out of 20%, we aimed to recruit 50 participants per study group.

Recruitment:

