Participants were recruited via contact lists of individuals who have volunteered in previous studies; organisations that ran group meetings within the target population, e.g. bridge clubs; and by flyers and posters at local community buildings, such as museums and libraries. All volunteers were initially screened for suitability by telephone or email, and they were sent a participant information sheet before coming to the University for the baseline test session. Screening was repeated at this test session, and consent completed. Participants were not informed of the aim of the study, but were instead told the project was studying habits and lifestyles in older adults.

Randomisation:

All eligible volunteers were randomized into one of two groups: intervention and control, following consent. Randomisation was stratified per ten year age group (55-64, 65-74, 75-85, 85+) and by earlier involvement in related research [ref], using blocks of 6-10 participants, with an exception that couples were always allocated to the same group. Randomization was undertaken by a researcher with no direct contact with participants ([name]).

Intervention

Community-dwelling older adults randomized to the intervention group received six high-protein egg-based recipes and herb/spice packets every two weeks to their home address, for twelve weeks. Recipes were intended to provide ideas for consuming eggs in different ways and using different flavours, to increase variety in the overall diet. Each recipe contained one or two eggs, and provided 25-30g of protein per meal.

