A schematic overview of the study design can be found in Figure 1. All participants came to Bournemouth University for a test session at baseline (T1), after 12 weeks intervention (T2), and after a further 12 weeks (T3). A week before each test session, participants received a set of questionnaires by post, to complete and bring to the test session. Queries were discussed at the test session, but on a few occasions, participants finished the questionnaires at home within a few days after the test session, and returned them by post. All test sessions were conducted in the morning between 8.00 and 11.00, at a time of the participant's preference. Participants came fasted, and were asked to have had only water to drink since going to sleep the night before the test session. Height and weight were measured first, followed by bioelectrical impedance measures of body composition. After these measures, a breakfast of toast / cereal and coffee / tea was provided. While the participant was eating breakfast, questionnaires were checked for missing values and any queries were discussed. After breakfast, the functional measures of lean muscle mass were undertaken. Questionnaires and tests undertaken were the same for each test session (T1, T2, T3), excepting that demographic and lifestyle characteristics, and reasons for eating / not eating eggs were only assessed at baseline. Test sessions were individual, or if preferred per couple, and lasted approximately an hour per person. After the baseline test session, all participants also received a postcard with a short dietary information message, including the importance of dietary protein for older adults and why it may be beneficial to eat more protein, and to do so for breakfast. This was included to add relevance to the recipes for those in the intervention group, but made no reference to the recipes or intervention, but was identical for all participants.

Blinding:

Outcome assessments were undertaken by a researcher who was blind to intervention group ([name]). Recipes and herb/spice packets were sent to intervention participants by a researcher with no direct contact with participants ([name]). Participants were not blind, although they were blind to the other possible conditions, thus the control group did not know about the intervention, nor the details of the intervention. Participants in the intervention group were asked not to mention the recipes to researchers.

Ethical Approval and Trial Registration

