Ethical approval for this study was granted by the Research Ethics Committee of Bournemouth University, prior to commencement. Participant recruitment started in May 2016, and test sessions were run from June 2016 to April 2017. The study was registered at ClinicalTrials.gov in May 2016 (NCT02777918).

Data analyses

Data were analysed using IBM SPSS Statistics for Windows, version 22, using an Intention-to-treat approach. First, all measures were tested for normality. All baseline measures were then compared

between the intervention and control group using χ^2 tests and Mann-Whitney U tests. Demographic and lifestyle characteristics were used to describe the sample. Correlations were investigated between all baseline measures. Multiple linear regression analyses were then used for the main analyses (Vickers & Altman, 2001). The effect of the intervention on all outcome measures was assessed using multiple linear regression, controlling for age, gender, baseline measures of the dependent variable, previous participation in related studies, and measures of total protein intake, BMI, usual physical activity and HR QoL score as assessed at the same time. Previous participation was included in regression models to allow for possible demand characteristics. Energy intake was not included in regression models following high correlations with BMI. Other demographic and lifestyle characteristics were also not included to maintain statistical power (Howell, 2012]. Separate regression models were used to predict egg intake, total protein intake, protein intake from animal sources, adverse events, lean body mass, physical performance, handgrip strength, and leg extensions as the dependent variables. Similar analyses were conducted once at the end of the 12 week intervention (T2) and once at the end of the following 12 weeks (T3). Egg intakes from the two different measures were compared using correlations and multiple linear regressions were conducted for both measures. Reasons for eating / not eating eggs and details on recipe feedback will be analysed further at a later date. These data and some of the data of participant demographic and lifestyle characteristics will be published elsewhere in exploratory analyses investigating intervention success / failure. Missing data were completed using last observation carried forward. Data are reported using means and standard deviations.

Figure 1: Schematic overview of the study design

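### Couples are allocated together, but the regressions treat every participant as independent, so standard errors are too small if partners' outcomes are positively correlated

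*Combined protocol and SAP*

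**What the plan says.** Under Randomisation, participants are randomised within strata of age and earlier research involvement, in blocks, "with an exception that couples were always allocated to the same group". The Procedure section indicates that couples did take part: "Test sessions were individual, or if preferred per couple". Under Intervention, participants in that arm "received six high-protein egg-based recipes and herb/spice packets every two weeks to their home address".

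Under Data analyses, "The effect of the intervention on all outcome measures was assessed using multiple linear regression". The covariates are age, gender, the baseline value of the outcome, "previous participation in related studies, and measures of total protein intake, BMI, usual physical activity and HR QoL score as assessed at the same time". None of these identifies a couple or household. Marital and living status were collected, but the other demographic and lifestyle characteristics were left out of the models, and neither variable would link two partners in any case. No random effect, estimating-equation method or cluster-robust standard error is named.

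The Sample size section states that "the required sample size to detect a 12.7g increase in protein intake in the intervention group equals 41 participants per group". It makes no mention of clustering.

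**The concern.** When two people always go to the same arm, their outcomes do not provide two independent pieces of information about the treatment difference unless they are uncorrelated given the covariates. Ordinary least squares assumes that they are. A positive residual correlation leaves the treatment estimate unbiased but makes its standard error too small, so confidence intervals are too narrow and false positives too frequent.

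The mechanism suits this trial. Recipes and packets arrive at a shared address, and partners are likely to share meals (an assumption). They would then tend to take up or ignore the recipes together. Adjusting for baseline does not remove a shared response to the intervention. The dietary primary outcomes (egg, total protein and animal protein intake) are therefore the most exposed. A residual correlation is less plausible for grip strength or lean mass, and there is no specific argument for it in adverse events.

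At stake is the reading of a borderline result on a primary dietary outcome.

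**Working it through.** **The plan's own figure.** Inputs from the Sample size section: difference 12.7 g, SD 20.3 g, alpha 5% (taken as two-sided), power 0.80.

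n per group = 2 × (1.960 + 0.842)² × 20.3² / 12.7² = 40.1, which rounds up to 41. This is the stated figure. It is the formula for independent observations, with no design effect.

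**Variance with couples.** Let c be the share of participants in couples and ρ the within-couple correlation left after covariate adjustment. An arm of n people contains cn/2 couples. The variance of the arm total is nσ² + (cn/2) × 2ρσ² = nσ²(1 + cρ). The variance of the treatment difference is therefore multiplied by

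DE = 1 + cρ.

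The ordinary standard error is too small by 1 − 1/√DE, and the actual two-sided type I error is 2 × [1 − Φ(1.96/√DE)].

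For example, c = 0.4 and ρ = 0.3 give DE = 1.12, 1.96/√1.12 = 1.852 and type I error 6.4%.

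**Results.** Both c and ρ are assumptions, because the documents give neither. The formula was checked by two simulations with no true effect and 50 per arm:
- A: baseline-adjusted regression, SD 20.3, assumed baseline correlation 0.5, ρ conditional on baseline, 20,000 replicates.
- B: regression with seven independent noise covariates, 10,000 replicates.

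| c | ρ | DE | SE too small by | Type I, formula | Type I, ordinary regression (A / B) | Type I, couple-clustered SE (A / B) |
|---|---|---|---|---|---|---|
| 0.1 | 0.2 | 1.02 | 1.0% | 5.2% | not run | not run |
| 0.2 | 0.3 | 1.06 | 2.9% | 5.7% | 5.6% / 5.8% | 5.1% / 5.5% |
| 0.4 | 0.3 | 1.12 | 5.5% | 6.4% | 6.6% / 6.3% | 5.3% / 5.2% |
| 0.4 | 0.5 | 1.20 | 8.7% | 7.4% | 7.4% / 7.5% | 5.5% / 5.5% |
| 0.6 | 0.5 | 1.30 | 12.3% | 8.6% | 8.4% / 8.3% | 5.2% / 5.4% |

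With no couples, simulation B gave 4.95% for the ordinary regression. In simulation A the ordinary standard error averaged 3.53 against an empirical 3.62 at (0.2, 0.3), and 3.51 against 4.01 at (0.6, 0.5). The clustered standard errors were 3.62 and 3.97.

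Coverage of a nominal 95% interval is 100% minus the type I error: 94.3% at DE 1.06 and 91.4% at DE 1.30.

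**Power.** For a valid unadjusted test at 41 per group, power is Φ(12.7 / (20.3 × √(2 × DE/41)) − 1.96): 78.6% at DE 1.06 and 70.0% at DE 1.30. Baseline adjustment works the other way, multiplying the variance by 1 − r², where r is the correlation between baseline and follow-up. Power of 80% returns when 40.1 × DE × (1 − r²) ≤ 41, that is r² ≥ 1 − 41/(40.1 × DE):
- DE 1.06: r² ≥ 0.036, r about 0.19.
- DE 1.30: r² ≥ 0.214, r about 0.46.

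If all 50 per group were analysed, the same formula without baseline adjustment gives 86% and 78%. The documents do not give r, so no power shortfall can be shown.

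**The case against.** The strongest objection concerns size. Couples are described as an exception, recruitment was partly through lists of individual volunteers, and nothing in the documents supports a share as high as 60%. By the formula above, type I error reaches 6% only when cρ is about 0.086, for example 29% of participants in couples at ρ = 0.3 or 43% at ρ = 0.2. Below that the excess is under one percentage point. This stands: the effect may be negligible, and the first row of the table deserves as much weight as the last.

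A second objection is that neither simulation uses the trial's covariates. The planned models adjust for total protein intake measured at the same time, which may absorb part of a shared household diet in the egg and animal-protein models. The residual correlation there could be below 0.3–0.5. This also stands, but it does not help total protein intake, which cannot be its own covariate. It lowers the plausible range without removing the mismatch.

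Third, testing ended in April 2017 and the analysis is described in the past tense, so the remedy is a re-analysis and not only a change of wording. That is right, but it does not make the remedy harder.

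None of this supplies what is missing. Without the number of couples, a reader cannot tell whether the effect is negligible.

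**Conclusion.** The concern holds as a conditional statement. Couples are allocated as pairs, the analysis takes no account of this, and nothing elsewhere in the document repairs it. Any positive residual correlation between partners makes the ordinary standard errors too small and pushes type I error above 5%.

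The size runs from negligible to moderate within the assumed ranges in the table. Clusters have at most two members, so the design effect cannot exceed 1 + ρ. The practical weight falls on total protein intake, then on egg and animal-protein intake, and less on the physical measures. The finding concerns the validity of intervals and tests. It does not show bias in the estimates or a failure of power.

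**What to change.** Refit each regression with standard errors clustered on couple or household, counting each single participant as a cluster of one. A household random intercept is an alternative, but its variance would be poorly estimated if couples are few, so clustered standard errors are the safer default. Report the number of couples in each arm, and state that the 41 per group assumes independent participants. If couples were few, the re-analysis will show that the conclusions are unaffected.

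The cost is small: one identifier that had to be known at allocation, a re-run of the existing models, and a sentence in the analysis section. The downside is slightly wider intervals if the correlation is positive. No further enrolment is needed.

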Our primary outcomes were egg intake, protein intake (total), protein intake from animal-based foods and adverse events. Secondary outcomes were lean body mass and various functional measures of lean body mass. Variables of potential influence on these outcomes were also assessed, to include various demographic and lifestyle characteristics, energy intake, BMI, usual physical activity levels, health-related quality of life, reasons for eating / not eating eggs, and recipe feedback (intervention group only) Morton et al., 2017). Some of these additional variables were included in analyses to control for potential confounding, some were used only to describe the sample and some were used to investigate further any reasons for intervention success or failure.

Primary Outcomes:

Egg intake: Egg intake was measured using two measures: an egg consumption Food Frequency Questionnaire (FFQ) measure [ref] and the egg section of a validated FFQ [SCG-FFQ, Clark, 2017; Masson et al., 2003]. The egg consumption FFQ requested frequency of consumption of 18 preparations of egg: boiled eggs (hot), hard boiled eggs (cold), fried eggs, scrambled eggs, poached eggs, omelettes, scotch eggs, quiches/savoury flans, egg sandwiches, egg salad, custards, meringues, sweet flan/crème caramel, duck/quail's eggs, raw eggs, egg yolk separate from the white, and egg white separate from the yolk. For each type of egg, participants were asked to complete number of measures (e.g. 1 egg, 1 slice) consumed per day (1, 2, 3, 4, 5+) on number of days per week, using response options 1 - 7 days per week, once or twice per month, or rarely / never. Responses were converted to number of eggs eaten per month, where the category 'rarely or never' was counted as 0 times eaten per month, 'once or twice per month' as 1.5 times, and 1 to 7 days per week, as 4, 8, 12, 16, 20, 24, and 28 times per month, respectively. All foods were considered to contribute equal portions of eggs, excepting the egg dishes custards, meringues, and sweet flan / crème caramel, where each consumption was considered as 0.5 portions, because a standard portion tends to be less than one egg.

The SCG-FFQ is a validated FFQ, developed by the Scottish collaborative group, measuring dietary intake over the last two-three months (Clark, 2017; Masson et al., 2003). The section on egg intake consists of

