three questions: number of measures (eggs) per day, and the number of days per week they eat 'Boiled or poached eggs'; 'Fried eggs'; and 'Scrambled eggs or omelette'. Response options were used and converted to monthly egg intake as above.

Protein intake: Protein intake was measured using the complete SCG-FFQ, where food intake data were converted to protein intake and protein intake from animal sources, by the Scottish collaborative group (Clark, 2017). Protein intake from animal sources consisted of protein intake from meat, fish, eggs, and dairy foods. Protein intake is known to be related to egg intake (Ruxton, Derbyshire, & Gibson, 2010, questionnaire study), to muscle mass, strength and function (Houston et al., 2008; Loenneke, Loprinzi, Murphy, & Phillips, 2016; Tieland et al., 2012), and to positive health outcomes in older adults (Hannan et al., 2000; Lord, Chaput, Aubertin-Leheudre, Labonté, & Dionne, 2007). Animal based proteins contain all essential amino acids and are considered high quality protein sources (van Vliet, Burd, & van Loon, 2015). Animal protein stimulates a higher net protein synthesis than a high plant protein diet (Pannemans, Wagenmakers, Westerterp, Schaafsma, & Halliday, 1998). These measures also allowed investigation of any replacement of other high protein foods by egg based protein foods.

Adverse events: To assess adverse events, participants were asked whether during the previous month they had experienced any of the following effects more or less often than usual: nausea, digestive issues (e.g. constipation or diarrhoea), stomach aches/cramps, hunger, bloating/uncomfortable fullness, thirst, headaches, fatigue/tiredness, restlessness, dizziness, or skin rashes. If they answered yes to any of these questions, they were asked if they knew of any reason for this, or they had experienced anything else that was different than usual.

Secondary Outcomes:

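### The primary intake outcomes are unranked and tested at T2 and T3 with no deciding test or multiplicity rule, although the trial is sized at an undivided 5% on total protein

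*Combined protocol and SAP*

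**What the plan says.** All references are to the combined protocol and SAP.

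- **Outcomes.** "Our primary outcomes were egg intake, protein intake (total), protein intake from animal-based foods and adverse events". The list has no order of importance. Under Primary Outcomes, egg intake is recorded in two ways: by a dedicated egg questionnaire and by the egg section of the general food frequency questionnaire (SCG-FFQ). Total and animal protein come from that same SCG-FFQ.
- **Data analyses, number of tests.** Each outcome has its own regression model. For egg intake, the two measures are correlated with each other and "multiple linear regressions were conducted for both measures". The analyses are run "once at the end of the 12 week intervention (T2) and once at the end of the following 12 weeks (T3"). No significance level, success rule, order of testing or adjustment is given.
- **Data analyses, covariates.** "The effect of the intervention on all outcome measures was assessed using multiple linear regression", and the listed covariates include "measures of total protein intake, BMI, usual physical activity and HR QoL score as assessed at the same time".
- **Sample size.** The calculation concerns daily protein intake only. It uses "an alpha of 5% for a power of 0.8" and is framed as follows: "Assuming no change in the control group over the intervention period". It arrives at 41 per group.

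**The concern.** The 5% in the sample-size calculation describes the risk of a false success claim only if one test decides. The sizing text points to total protein at the end of the intervention, but neither Outcomes nor Data analyses designates it. Those sections give the egg measures, animal protein and T3 the same standing. With no rule, nothing prevents a conclusion of success from resting on whichever intake result turns out significant.

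The outcomes can also disagree in a way the plan itself foresees. The Primary Outcomes text says the protein measures allow study of whether eggs displace other protein-rich foods. If they do, egg intake rises while total protein does not, and the plan does not say which result answers the trial's question.

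The covariate list raises a second, related problem. Same-visit total protein is itself a primary outcome that the intervention is meant to raise. An egg or animal-protein model that holds it constant does not estimate the total effect of the intervention.

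**Working it through.** **1. Reproduce the plan's figure.** Inputs from Sample size: difference 12.7 g/day (midpoint of 75–90, less the survey mean: 82.5 − 69.8), SD 20.3 g/day, alpha 5%, power 0.8.

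n per group = 2 × (1.960 + 0.842)² × (20.3 / 12.7)² = 2 × 7.85 × 2.555 = 40.1, rounded up to 41.

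The standardised difference is 12.7 / 20.3 = 0.626, and a two-sample t-test with 41 per group has power 0.799. A one-sided 5% test would need only 32 per group by the same formula. The stated 41 therefore corresponds to a two-sided test with the whole 5% spent on protein intake.

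**2. Count the intake tests at T2.** Counting egg intake once gives three: egg, total protein and animal protein. Counting both egg measures, as Data analyses does when it fits a regression to each, gives four. Adding T3 to the four gives eight. Adverse events are left out, because a difference there would not be a claim that the intervention worked.

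**3. Chance of at least one false positive.** Assumptions not in the documents: each test is two-sided at 5%, no intake outcome is affected, any significant result is read as success, and the test statistics share a common correlation r.

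For r = 0 the formula is 1 − 0.95^m:
- m = 3: 1 − 0.857 = 0.143
- m = 4: 1 − 0.815 = 0.185
- m = 8: 1 − 0.663 = 0.337

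For r > 0, each statistic is written as √r × C + √(1 − r) × E, with C a shared and E a separate standard normal variable, and the rate is the proportion of draws in which any |Z| exceeds 1.96 (1,000,000 draws):

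| Tests | r = 0 | 0.3 | 0.5 | 0.7 | 0.9 |
|---|---|---|---|---|---|
| 3 (T2, egg counted once) | 0.143 | 0.136 | 0.125 | 0.109 | 0.083 |
| 4 (T2, both egg measures) | 0.185 | 0.175 | 0.156 | 0.130 | 0.094 |
| 8 (the four at T2 and T3) | 0.337 | 0.301 | 0.250 | 0.191 | 0.119 |

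**4. Where in the range?** The documents give no correlations, but they show overlap. "Protein intake from animal sources consisted of protein intake from meat, fish, eggs, and dairy foods", so animal protein is a component of total protein and includes egg protein. One egg measure is a section of the same questionnaire. Both facts favour the right-hand columns. Covariate adjustment may alter the correlations, so no single value can be fixed.

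**5. The covariate, read literally.** If same-visit total protein enters every model, the total-protein model contains its own outcome as a predictor, fits perfectly and leaves no treatment effect to test. Three informative T2 tests would remain (two egg measures and animal protein), again 8–14%. Counting total protein as a valid test assumes that it was not a covariate in its own model.

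**The case against.** The strongest reply is that the plan never says any one significant result is enough. It states no success rule at all, names every model in advance and runs all of them, which is not the same as choosing a winner. That stands: the percentages are conditional on a rule that a reader would have to supply.

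It can also be said that the two egg measures are one outcome checked for agreement, since the plan correlates them. That is a fair alternative reading, and it is why the three-test figure is given beside the four-test figure. It does not remove the ambiguity, because both measures are regressed and neither is preferred.

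Three stronger inferences are tempting, and the documents do not support them:

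- *A reader might infer a false-success risk of 34%.* That needs eight independent tests with T3 given equal weight. The measures overlap, and the sizing text refers only to the intervention period, while T3 falls 12 weeks after it ends.
- *A reader might infer that the sample size is wrong.* It reproduces, and it remains adequate if one test is designated.
- *A reader might infer that total protein was actually fitted with itself as a covariate.* The text says so only if its general covariate list is applied without exception. What the text establishes is that the list needs correcting.

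Finally, sessions ended in April 2017 and the document is dated July 2018, so any ordering introduced now comes after the data. That limits what a remedy can achieve, but it is a reason to disclose the missing hierarchy rather than leave it unstated.

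**Conclusion.** The concern holds as a gap in the plan: primary intake outcomes without ranking, success rule or multiplicity adjustment, beside a sample size that commits an undivided two-sided 5% to protein intake over the intervention period.

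If any significant T2 intake result is taken as success, the false-positive risk is about 8–14% or 9–19%, depending on how egg intake is counted. Counting T3 equally raises it further. Even at a correlation of 0.9 it is well above 5%. The ranges rest on the assumed rule, a 5% two-sided level per test and assumed correlations, so they bound the problem without fixing its size. They do not show that any reported result is false.

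The covariate wording is a separate defect. Read literally, the egg and animal-protein models do not estimate the total intervention effect, and the total-protein model is uninformative. The plan should be corrected on both counts. Confidence is medium.

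**What to change.** 1. Make total protein at T2, the outcome and period the trial was sized on, the single deciding test at two-sided 5%.
2. Only if it is significant, test both egg measures and animal protein at T2 with Holm adjustment (smallest p-value against 0.05 / 3 = 0.0167, then 0.025, then 0.05). This holds 5% overall. If total protein is unaffected, any false claim first requires a 5% event; if it is affected, Holm limits error among the other three to 5%. Running the Holm family regardless of the total-protein result would leave about 6–10% across both steps when no outcome is affected.
3. Treat T3 as secondary. Report adverse events as between-group estimates with confidence intervals.
4. Report all ten results: eight intake (four measures at two visits) and two for adverse events.
5. Remove same-visit total protein as a covariate from the total-protein, egg and animal-protein models.
6. State that this ordering was set after data collection, unless an earlier record fixes it.

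**Cost.** No new data are needed, only relabelling, refitting the intake models and adjusting three p-values. The 41 per group stands. By comparison, splitting alpha equally over four tests (0.0125 each) would need 57 per group for total protein, or leave 63% power at 41, by the normal approximation.

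The egg and animal-protein results lose stand-alone primary status and some power, and the documents give no basis for a figure. If eggs merely displaced other protein, a rise in egg intake could be described but not claimed as confirmed. An ordering set after the data does not carry full prespecified error control.

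Same-visit BMI, physical activity and quality of life are also measured after randomisation. They need separate treatment and are not resolved by this change.

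### Separate egg yolk and separate egg white are left out of the half-portion rule, so each part-egg counts as a whole egg in one of the two egg-intake measures

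*Combined protocol and SAP*

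**What the plan says.** Egg intake is a primary outcome with two measures, an egg consumption FFQ and the egg section of the SCG-FFQ. For the first, Primary Outcomes (Egg intake) fixes the unit: "Responses were converted to number of eggs eaten per month, where the category 'rarely or never' was counted as 0 times eaten per month". Weekly frequencies are converted from "1 to 7 days per week, as 4, 8, 12, 16, 20, 24, and 28 times per month, respectively".

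The weights follow: "All foods were considered to contribute equal portions of eggs, excepting the egg dishes custards, meringues, and sweet flan / crème caramel". The three exceptions are entered at half, "where each consumption was considered as 0.5 portions, because a standard portion tends to be less than one egg". The list of preparations in the same paragraph ends with "egg yolk separate from the white, and egg white separate from the yolk". These two are not among the exceptions and so carry full weight.

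The Data analyses section runs the regressions for both egg measures and adjusts for the baseline value of the dependent variable.

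**The concern.** The plan gives one reason for the half weight: the portion holds less than one egg. For the three sweet dishes this is a judgement about a typical portion. For a yolk without its white, or a white without its yolk, it is true by definition. The rule therefore leaves out the two items to which its own reason applies most clearly.

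At stake is the count itself. The outcome is read as a number of eggs, and anyone who reports separate yolks or whites is credited with more eggs than they ate. If use of these items came to differ between the groups during follow-up, part of the group difference on this measure would come from the scoring.

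**Working it through.** **Inputs**, all from Primary Outcomes (Egg intake):
- unit: eggs per month
- default weight 1; exception weight 0.5 for three sweet dishes
- separate yolk and separate white: listed, not excepted, so weight 1

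**1. The plan's conversion.** Days per week x 4 gives 4, 8, 12, 16, 20, 24, 28 for 1 to 7 days, as stated.

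**2. One egg, separated, both parts eaten, one day a week, one measure of each reported.**
- Planned rule: 4 x 1 + 4 x 1 = 8 per month.
- Eggs used: 4 per month.
- Weight 0.5 each: 4 x 0.5 + 4 x 0.5 = 4 per month.

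The planned rule is too high by 8 / 4 = 2 for these items. If only one part is eaten, it gives 4 x 1 = 4 against 4 x 0.5 = 2, again a factor of 2.

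**3. Effect on total eggs per month.** Let R be the recorded total and s the share of R from the yolk and white items. The corrected total is R(1 - s) + R x s/2 = R(1 - s/2), so recorded / corrected = 1 / (1 - s/2). The documents do not give s, so it is varied:

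| Assumed s | Recorded / corrected |
|---|---|
| 2% | 1 / 0.99 = 1.01 |
| 5% | 1 / 0.975 = 1.03 |
| 10% | 1 / 0.95 = 1.05 |
| 25% | 1 / 0.875 = 1.14 |
| 50% | 1 / 0.75 = 1.33 |
| 100% | 1 / 0.5 = 2.00 |

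As an illustration, 20 other eggs a month plus one white a week scores 20 + 4 = 24 against 20 + 2 = 22, and 24 / 22 = 1.09.

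**4. Effect on an unadjusted group difference.** Halving the weight takes half of the yolk and white score out of each group's mean. The recorded difference is therefore off by half of the between-group difference in that score. It is off by nothing if the groups use these items equally. The documents give no intake by item, so neither sign nor size can be stated.

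**The case against.** The case for leaving this alone is reasonable. One rule is applied to both groups at all three sessions, and the models adjust for baseline. Separate yolks and whites may be a small part of intake. The 8-for-4 example needs a respondent to report both halves of the same egg. The intervention effect is also estimated on the SCG-FFQ egg section, which asks only about boiled or poached, fried, and scrambled eggs or omelette, and whose measure is the egg. All of this stands and limits the size of the problem. It does not make the rule consistent with its stated reason.

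A reader might also infer three stronger points, which the documents do not support:

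- **That a dish scores the same with one egg or two.** The Intervention section says "Each recipe contained one or two eggs, and provided 25-30g of protein per meal", which invites this reading. But the egg FFQ also asks how many measures are taken per day, with one egg as its first example. A two-egg omelette on two days a week can be entered as 2 measures, giving 2 x 8 = 16 if times are multiplied by measures. The conversion text does not spell out that multiplication, which is a separate reporting question. Nothing says that dishes are reported by the dish.
- **That quiche or savoury flan should count 0.5 because sweet flan does.** The documents give no egg content for a portion of either, so the difference in weight is not shown to be an error.
- **That the scoring shrinks the group difference.** This rests on the first point, or on the intervention changing use of yolk and white items. Neither is shown.

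**Conclusion.** The point holds for two items in one of the two egg measures. Separate yolk and separate white score as whole eggs although the plan's own reason for the 0.5 weight covers them.

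The factor of two is a bound for those items. It should not be read as an error of that size in eggs per month: the total doubles only if the whole recorded intake is separate yolks or whites. At assumed shares of 2% to 10% the total is overstated by about 1% to 5%. The true share is not in the documents.

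The equal 0.5 split is an assumption. It is the weight the plan already uses for portions below one egg, and it makes the two parts add up to one egg. The error distorts the absolute count; a bias in the comparison between groups is not established.

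**What to change.** Add separate yolk and separate white to the items weighted 0.5. Re-score the egg consumption FFQ at T1, T2 and T3 from the stored item responses, rerun its regressions, and report the planned score beside the corrected one. Giving the share of recorded intake from these two items would let readers judge the size directly.

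The cost is a short re-scoring run on data already held. The small downside is that the corrected counts are not directly comparable with work that used the present scoring; showing both scores deals with that.

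A 0.5 weight for quiche and savoury flan belongs at most in a sensitivity analysis. Dish items should not be bracketed at weights of 1 and 2, because that would double-count anyone who entered eggs as measures: the omelette already scored 16 would become 32.
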